Trial Selection of participants and sampling. Participants were recruited from Hazelden Betty Ford Foundation (HBFF) and Lifeworks NW in the Portland metro area, which offer inpatient and intensive outpatient (IOP) treatment for SUD. Facilities under HBFF included one residential and one IOP clinic, and facilities under Lifeworks NW included two residential and one IOP clinic, totaling five clinics. Criteria for admittance into all facilities include a dual-diagnosis for substance use disorder (SUD) and another mental health disorder. Approximately 95% of women within these treatment facilities have a lifetime history of trauma, and approximately 88% are dually diagnosed with SUD and PTSD. As part of the standard care at the residential sites at HBFF and Lifeworks NW, patients undergo a detoxification treatment phase upon admission, followed by a “core learning” phase in which patients participate in group and individual therapy. They then move into a “transition phase” during which they prepare an aftercare plan, and secure both sober housing accommodations and partial employment and/or enrollment in an educational institute or trade school. Patients enrolled in HBFF and Lifeworks NW IOP have already undergone detoxification and are required to participate in groups, individual therapy and case management; treatment completion is between eight and 12 months.

Patients in the core learning phase of residential treatment, and patients in IOP were recruited for the study. Patients in residential programs were physically stable after the detoxification phase, and able to participate in groups. The core learning phase of treatment within residential facilities typically begins two to three weeks after detoxification and lasts for approximately three months. Counselors and administrators of both residential and IOP clinics assisted with recruitment via word of mouth, flyers, and announcements at weekly group meetings. Data was monitored during the recruitment process and additional effort was made to

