recruit ethnic and racial minority groups when necessary. To be included in the study, individuals 1) were in the “core” phase of treatment or in IOP at LWNW or HBFF; 2) scored at least a four or higher on Breslau’s Short Screening Scale (Kimberling et al., 2006) for PTSD; 3) were between 18 and 70 years of age; 4) were fluent in speaking and reading English; and 5) had clearance from appropriate clinical staff. Individuals were excluded from study participation if they 1) endorsed active suicidality, hallucinations, or intense emotional lability; 2) had already participated in an MBRP group in current or past treatment; and 3) did not provide informed consent. Inclusion and exclusion criteria were assessed by the Inclusion/Exclusion Screening Tool.

Sample size estimation. For a fully-powered, cluster-randomized design, a power analysis conducted via G*Power (Faul, Erdfelder, Lang, & Buchner, 2007) using $\alpha = .05$, medium effect size across primary outcomes, mediators and moderators, a variance inflation factor of 2.55, and power level of .8 suggests a sample size of 437 participants (Donner, 1998). As a feasibility and initial efficacy trial, it is justified to recruit 10% of what is required of a fully powered clinical trial (Cocks & Torgerson, 2013; Treece & Treece, 1977); thus, we aimed to recruit 44 participants. Due to high attrition rates (56%) at a 15-week follow-up from previous research at the Phase I clinical sites (Witkiewitz, 2014), we aimed to recruit 100 participants to secure a sufficient sample size at one-month follow-up powered to analyze primary outcome data at the end of intervention implementation. We aimed for an attrition rate of 40% or less due to the short duration of the study and greater ease in contacting participants at follow-up due to most participants’ residential and active IOP status. Mediators and moderators were not included in the power analysis due to the current study being a feasibility and initial efficacy trial, and the

exploratory intention of examining mechanisms and moderators for a future, fully-powered study.

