One month after the completion of post-course assessments, participants were asked to complete a follow-up assessment battery. If participants were unable to be physically present to complete the follow-up assessment, they were offered a phone interview during which an RA administered self-report assessment measures orally.

Participants were given a \$20 gift card (not redeemable for alcohol, cigarettes, or lottery tickets) at completion of each of the first two assessments (i.e., baseline assessment, post-course assessment) and post-course focus group. A \$40 gift card was provided at completion of the one-month follow-up assessment. Total possible compensation for participation in the study was \$100.

Design and analyses. This study is an initial step in exploring the safety, feasibility, and acceptability of a novel adaptation to an evidence-based intervention. We employed a cluster-randomized, mixed methods, repeated measures design to determine feasibility, acceptability, initial efficacy, and mediators and moderators for TI-MBRP for women with co-occurring SUD and PTSD. Data from this study will inform the ecological validity and any further modifications that need to occur to the adapted protocol before conducting a larger cluster-randomized trial (Leon, Davis, & Kraemer, 2011; Moore, Carter, Nietert, & Stewart, 2011). Furthermore, determining initial efficacy and mediators and moderators will inform whether integrating

evidence-based trauma education and interventions into MBRP will reduce PTSD symptom severity and substance use indices in dually diagnosed women with PTSD-SUD more efficiently than SUD treatment alone, and inform which measures to test as mechanisms and moderators in a larger trial (Leon, Davis, & Kraemer, 2011).

Paper-and-pencil, self-report measures used at baseline, post course, and follow-up assessment points, as well as records of attendance, were double-entered into SPSS 26.0 by RAs. Prior to conduction planned quantitative analyses, data was checked for normality (skew +/- 2, kurtosis +/-2), homogeneity ($p < .05$), and accuracy using the exploratory function in SPSS (Fields, 1999). Outliers were assessed by identifying studentized residuals greater than ± 3 standard deviations. Although missing data is expected in this population, Restricted Maximum Likelihood Estimations (RMLE) allow for all participants to be included in analyses even if they present with missing data.

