Feasibility and acceptability was assessed using multiple metrics. Based on completion rates of an RCT conducted at the Phase I clinical site (Witkiewitz et al., 2014), we assessed recruitment and retention rates, with a target rate retention of 60% or better. Participant overall course satisfaction was measured by the OCSS. Treatment dropout was monitored by tracking attendance at each session and information will be gathered from clinical sites to determine whether the participant dropped out of treatment altogether or the study. This will allow assessment of any systematic bias or characteristics of TI-MBRP drop-outs vs. course completers.

To assess initial efficacy, Repeated Measures Analysis of Variance (RM ANOVA) was used to examine differences between TI-MBRP and Standard MBRP in substance use, craving, and PTSD symptoms over time. When an interaction effect was detected, an ANCOVA was used

to determine the timepoint in which two conditions differed, controlling for baseline scores (Fields, 1999). Mediators and moderators were examined using PROCESS in SPSS 26.0 to help identify factors that explain or support change in the relationships between PTSD symptom severity and craving, and PTSD symptom severity and substance use.

For Phase II qualitative data collection and analyses, ten one-hour long focus groups were audio recorded once participants completed either TI-MBRP or Standard MBRP. Women were asked eight questions to assist with the refinement of the pilot protocol (See Appendix .

Questions were as follows:

1. What was your overall experience like in this group?
2. How did this class help with understanding the relationship between substance use and trauma?
3. How did this class help with processing the impact of traumatic events on aspects of your life now?
4. How was this group different or similar from other substance use and trauma groups you have completed in the past?
5. Is there anything that you felt was missing from this program that would have enhanced your experience while taking this course?
6. What aspects of the treatment did you find helpful and/or important in your recovery process?
7. What aspects did you dislike and feel could be changed or taken out?
8. Would you recommend this group to other women who have not taken it yet?
9. How would you describe the group to other women who have not taken this group yet?

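### Substance use is tested by a repeated-measures interaction that also decides whether the baseline-adjusted comparison is run; if most women report no use, that test is weak and the plan names no alternative

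*Combined protocol and SAP*

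**What the plan says.** All references are to Phase II of the Combined protocol and SAP.

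- **Efficacy model (Design and analyses).** One method serves all three outcomes: repeated-measures ANOVA "was used to examine differences between TI-MBRP and Standard MBRP in substance use, craving, and PTSD symptoms over time". No separate model is given for substance use.
- **Baseline adjustment (same section).** It is conditional: "When an interaction effect was detected, an ANCOVA was used" to locate the time at which the arms differ, with baseline as covariate.
- **Data checks (same section).** Before analysis, "data was checked for normality (skew +/- 2, kurtosis +/-2", and "Outliers were assessed by identifying studentized residuals greater than ± 3 standard deviations". Nothing is said about what follows if a check fails or a value is flagged.
- **Setting (Selection of participants and sampling).** At the residential sites "patients undergo a detoxification treatment phase upon admission", and recruitment comes later, in a core phase of about three months. IOP patients are also past detoxification, and their treatment runs eight to 12 months. Three of the five clinics are residential.
- **Status at follow-up (Sample size estimation).** The plan expects to reach women easily because of most participants' "residential and active IOP status".
- **Timing (Procedures).** Eight sessions take four weeks, post-course assessment comes within a further week, and follow-up is a month after that.

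**The concern.** Craving and PTSD scores can vary among all women at all three times. Substance use in women who are past detoxification and still in treatment is likely to be zero for many of them after baseline, with a few scattered positive values. An interaction F test on such data compares mean changes, and those means depend on a handful of women.

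The sequence of tests adds to the problem. The analysis that adjusts for baseline runs only after the interaction test succeeds, so the weaker test decides whether the better one is used. If baseline asks about use before admission, it is also the time point with most of the spread, and chance differences at baseline then supply most of the noise in the interaction.

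Substance use is one of three efficacy outcomes of a relapse-prevention course, and the results are meant to inform a larger trial. A null interaction could be read as no effect on use when the test had little chance of showing one.

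**Working it through.** **Inputs from the plan.** The retained sample follows from Sample size estimation: 10% of 437 = 43.7, so 44; 44/(1 − 0.56) = 100 to recruit; at 40% attrition, 100 × 0.60 = 60. I use 44 and 60 women, or 22 and 30 per arm. (The 437 does not follow from a two-group comparison at d = 0.5, which gives 128 × 2.55 = 326. The test behind it is not stated, and nothing here depends on it.) Alpha is 0.05; two-sided testing and 1:1 allocation are assumed.

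**Assumptions.** The outcome is days used in 30. At each later time 20% use in one arm and 5% or 10% in the other; users report 1 to 15 days, evenly spread. Use at the two later times is either independent or by the same women. Baseline is either pre-admission (mean 12, SD 8) or near zero. There is no cohort effect.

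**1. Any-use comparison.** With n per arm and p̄ the mean of the two proportions,

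power = Φ{[(p1 − p2)√n − 1.96√(2p̄(1 − p̄))] / √[p1(1 − p1) + p2(1 − p2)]}.

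If the same women use at both times, any use is 20% v 5%. If use is independent, it is 1 − 0.8² = 36% v 1 − 0.95² = 9.75%. For 20% v 10%, the independent case is 36% v 1 − 0.9² = 19%. The last column divides n by the plan's variance inflation factor of 2.55.

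| Use per time | Pattern | n = 22 | n = 30 | Same, with 2.55 |
|---|---|---|---|---|
| 20% v 5% | same women | 32% | 42% | 15%, 19% |
| 20% v 5% | independent | 55% | 69% | 24%, 32% |
| 20% v 10% | same women | 15% | 19% | 8%, 10% |
| 20% v 10% | independent | 24% | 31% | 12%, 15% |

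Simulation of the score test gives 33–71% and 15–32% without clustering.

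**2. RM ANOVA interaction.** Simulated 2 × 3 design with Greenhouse-Geisser correction:

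| Use per time | Pre-admission baseline | Near-zero baseline | Any-use test |
|---|---|---|---|
| 20% v 5% | about 8–9% | about 11–20% | 33–71% |
| 20% v 10% | about 5–7% | about 7–11% | 15–32% |

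The any-use test is ahead under both baseline windows. With no true effect, the corrected interaction rejects in about 5% of runs or slightly fewer.

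**3. Baseline share of the contrast.** Take the contrast as baseline against the mean of the two later times. Share = V(baseline)/[V(baseline) + V(later mean)].

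- Pre-admission: V(baseline) = 8² = 64. For days 1 to 15, the mean is 8 and the mean square 82.67. At 20% use, one later value has variance 0.2 × 82.67 − 1.6² = 13.97. Independent use gives 13.97/2 = 6.99, and the share is 64/70.99 = 90%. With the same women using, the covariance is 0.2 × 0.8 × 64 = 10.24, V(later mean) = (13.97 + 10.24)/2 = 12.1, and the share is 64/76.1 = 84%. Simulations with longer-tailed amounts and use from 10% to 50% give 91–98%.
- Baseline within treatment, same distribution and independent: 1/(1 + ½) = 67%. Any outcome with independent times would show this.

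**4. The plan's own checks.** Under these amounts the skew of a later value is 2.3 at 20% use and 3.7 at 10%; with longer-tailed amounts it is about 3.3 and 4.4. All exceed the limit of 2, and no alternative follows. For the residual screen, if x of n women use the same amount, a user's studentized residual is √[(n − x)/x]: 4 of 44 gives 3.16, 5 of 44 gives 2.79, and 6 of 60 gives exactly 3.0. With amounts of 1 to 15 days, about 40% of users are flagged at 10% use and about 61% at 5%.

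**The case against.** The strongest reply is that this is a pilot sized at a tenth of a full trial, so low power is expected for every outcome. A continuous outcome at d = 0.5 with 30 per arm has 48% power, or 23% with the variance inflation factor. The any-use gain also looks best at a large contrast, 20% v 5%, against an active comparator and without clustering. All of that stands, and it limits what any method can show. It does not remove the loss from the choice of test, which appears at the same sample size under both baseline windows and for the smaller contrast.

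Several stronger readings are tempting and go beyond the documents.

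- **That most women will certainly report no use.** No rate is given. The remark about treatment status explains ease of contact, not abstinence. IOP women are outpatients, and some residents may have left the core phase by follow-up. The plan elsewhere speaks of substance use indices, so the measure may be a severity score rather than days.
- **That a detected interaction would usually be a baseline difference between arms.** This needs a pre-admission window, which is not stated, and it overlooks the ANCOVA that follows. With no true effect, a significant interaction followed by a significant ANCOVA occurs in at most about 3% of simulated runs.
- **That the false-positive rate is inflated.** Rates of 6–9% come from the F test without a sphericity correction; with it the rate is near 5%. Baseline imbalance adds noise, not bias.
- **That every woman who uses lies beyond 3 SD.** This needs all users to report the same amount and fewer than 10% to use. Nor does the plan say that flagged values are removed.

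**Conclusion.** The point holds in conditional form. The plan gives substance use the same interaction test as the symptom scores and makes baseline adjustment depend on it, with no stated measure, recall window or method for an outcome that may be mostly zeros. If about 20% or fewer use at each later time, the interaction has roughly 5–20% power over the settings examined, against 15–71% for any use, before clustering. With the plan's inflation factor, any-use power falls to about 8–32%, so neither analysis would be decisive; this is why an estimate with an interval serves better than a test. If baseline looks back before admission, some 84–98% of the variance of the baseline-versus-later contrast is baseline noise. These figures rest on an assumed days-of-use measure, assumed rates and amounts, and 44 to 60 women retained. This should be changed, because a better method is available at little cost.

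**What to change.** 1. Do not use the repeated-measures interaction as the test of substance use, or as the gate to further analysis of it.
2. State the substance-use measure and its recall window at each assessment.
3. Report any use (yes/no) by arm over the period covered by the post-course and one-month self-reports, as a risk difference with 95% CI. The interval should respect the randomised cohorts, and the estimate should adjust for residential versus IOP at enrolment.
4. As support, report the amount of use at each later time adjusted for baseline, with a count or two-part model if the measure is days of use.
5. For this outcome, use the 3 SD flag only to check data entry.
6. Keep the repeated-measures analysis for craving and PTSD symptoms.

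The cost is analysis-plan wording and a re-run on data already collected, provided the self-reports record use or days of use; enrolment setting is known from the recruiting clinic. There are two drawbacks. Any use ignores the amount used, which item 4 partly covers. It also cannot be determined for women lost to follow-up, so the number missing should be reported by arm.

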COVER PAGE

Title: A trauma-Informed Adaptation of Mindfulness-Based Relapse Prevention for Women in
Substance Use Treatment

NCT03505749

Document Date: 02/29/2020

PROCEDURES AND STATISTICAL ANALYTIC PLAN

This goal of this study was to develop and implement an integrated intervention protocol for a feasibility and initial efficacy trial of TI-MBRP. During the treatment development phase, information was gathered from focus groups with counselors and patients. The trial determined feasibility, acceptability and initial efficacy, explored mediators and moderators of change, and informed the design for a larger randomized-control trial.

The study was executed in two phases. The first phase consisted of intervention development and refinement. Intervention development was accomplished by conducting three focus groups with counselors and patients of a chemical dependency treatment center for women in which standard MBRP is a required part of programming. The purpose of these focus groups was to gather themes associated with trauma and substance use (e.g., avoidance of PTSD symptoms and function of substance use as it relates to PTSD, craving, guilt/shame, self-esteem). Information gathered after each Phase I focus groups was integrated into the standard MBRP protocol, along with aspects of CPT. Each protocol modification was presented to participants at subsequent Phase I focus group meetings for feedback and further refinement of the protocol until a final pilot adaptation was created. The pilot protocol underwent three revisions with participants' feedback. Phase II of the study consisted of a feasibility and initial efficacy trial using the refined intervention, and collection and assessment of feasibility and preliminary outcome data.

Phase I: Intervention Development and Refinement

Counselors and residents from the Volunteers of America Women's Residential Center (WRC) were recruited for a series of focus groups to assist with the development and refinement of TI-MBRP. Attending separate groups to ensure confidentiality, counselors and residents with previous experience in MBRP groups discussed how trauma-related symptoms and issues have

manifested during MBRP sessions, and offered suggestions, reflections, and concerns regarding the appropriateness and acceptability of integration of trauma education and treatment approaches into MBRP. Information collected during these focus groups informed the initial adaptation of the intervention.

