endorsed a four or higher on the BSSS and met inclusion criteria, they were offered participation in the study. Interested patients also had clearance from their primary counselors to confirm they did not meet exclusion criteria. Eligible individuals were provided with a written and oral informed consent. The PI or RA reviewed the informed consent and answer any questions or concerns that individuals had about study procedures, confidentiality, data analysis, and dissemination of results. Once written informed consent was obtained, participants were notified of the group start date within one week of signing the consent form. Participants were asked to complete a battery of paper-and-pencil assessments within one week prior to the start of the first session. After assessments were completed, cohorts of participants were randomized to receive either Standard MBRP or TI-MBRP. A non-interventionist RA used computer randomization software to assign to cohorts to either Standard MBRP or TI-MBRP. Ten TI-MBRP and Standard MBRP groups were implemented simultaneously at five sites for maximization of participants within the given timeframe over a 12-month period.

After the first Standard MBRP and TI-MBRP session, participants were provided with a CD player and CD with audio-recordings of guided meditation practices used in the intervention (i.e., body scan, breath awareness) to use daily as a part of their homework requirements. Cohorts randomized to the TI-MBRP group were given an additional CD with mindfulness practices administered only in the TI-MBRP course.

Participants completed a post-course assessment battery within one week of the completion of the eight-session course, taking place over four weeks. They had access to doctoral level psychology graduate students and to their primary counselor to discuss any distressing feelings related to the study.

One week after post-course assessments, participants were invited to participate in a focus group to discuss what was helpful about the intervention and what could be changed. Focus groups were audio-recorded, transcribed, and analyzed in NVivo Pro V12. Frequently discussed topics within focus groups were used to inform changes to the pilot protocol which will optimize interventions within TI-MBRP targeting craving, substance use and PTSD symptoms.

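### The baseline-adjusted arm difference is estimated only after a detected interaction, so it is missing for the other outcomes and tends to be too large where it is given

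*Combined protocol and SAP*

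**What the plan says.** The efficacy paragraph of Design and analyses (Phase II) applies a repeated measures ANOVA, without any condition, to "differences between TI-MBRP and Standard MBRP in substance use, craving, and PTSD symptoms over time". The next step is conditional: "When an interaction effect was detected, an ANCOVA was used" and its purpose is "to determine the timepoint in which two conditions differed, controlling for baseline scores". There are three assessments: baseline, post-course and one-month follow-up.

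Nothing else in the document supplies the adjusted arm contrast without the condition. The restricted maximum likelihood sentence concerns missing data and names no contrast. The PROCESS analyses concern how PTSD severity relates to craving and to substance use. No confidence interval for an arm difference is planned.

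The threshold for a detected interaction is not stated. The .05 under Sample size estimation belongs to the power calculation, and the .05 under Design and analyses belongs to the homogeneity check.

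Procedures puts baseline before allocation: "After assessments were completed, cohorts of participants were randomized to receive either Standard MBRP or TI-MBRP". The opening section says the trial "informed the design for a larger randomized-control trial".

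**The concern.** The interaction test and the ANCOVA use the same data. Reporting the ANCOVA only when the test is positive keeps the samples in which the arms happened to differ most. Two things follow. A real effect may leave no adjusted estimate at all, and the estimates that do appear are biased away from zero.

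The condition is not needed for estimation. Baseline was measured before cohorts were allocated, so the adjusted difference can be estimated for every outcome.

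This matters more in a pilot than in a full-size trial. A study at about one tenth of full size will often miss a real effect, so its useful efficacy output is a complete set of estimates with intervals. If the gated estimates were used to plan the next trial, that trial would tend to be too small. The document does not say they will be used in this way.

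**Working it through.** **Inputs from the document (Sample size estimation)**
- Minimum target: 10% of 437 = 43.7, rounded to 44.
- Recruitment target: 44 / (1 − 0.56) = 100. The plan's own figure reproduces.
- Retained at the attrition goal ("We aimed for an attrition rate of 40% or less"): 100 × (1 − 0.40) = 60.
- Effect: described as medium, with no metric. Taken here as d = 0.5.

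**Assumptions**
- A smaller effect, d = 0.3, is added.
- Within-person correlation ρ is .5, .7 or .85.
- SD is 1, with the same correlation between all pairs of times and the same effect at both follow-ups.
- Arms are equal, data are complete and there is no clustering.
- The gate is the F test at .05.

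**Step 1: how often the gate stays closed.** The true arm differences at the three times are (0, d, d). Their sum of squares about their mean is (2/3)d². The interaction F test has 2 and 2(n − 2) degrees of freedom and noncentrality

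λ = (n/4) × (2/3)d² / (1 − ρ).

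For n = 60, d = 0.5, ρ = .5: λ = 15 × 0.1667 / 0.5 = 5.0. The power is 49%, so the estimate is withheld in 51% of trials.

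**Step 2: what the ANCOVA gives when the gate opens.** In 20,000 simulated trials per setting, the one-month difference was estimated by regressing the outcome on arm and baseline, and averaged over the trials with a detected interaction. Simulated withheld rates agree with the formula to within about one percentage point.

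| n | true d | withheld (ρ = .5 / .7 / .85) | mean estimate when given | ratio to truth |
|---|---|---|---|---|
| 60 | 0.5 | 51% / 28% / 4% | 0.61 / 0.56 / 0.51 | 1.22 / 1.12 / 1.02 |
| 60 | 0.3 | 80% / 69% / 43% | 0.48 / 0.44 / 0.37 | 1.61 / 1.48 / 1.23 |
| 44 | 0.5 | 63% / 42% / 12% | 0.66 / 0.60 / 0.53 | 1.32 / 1.21 / 1.06 |
| 44 | 0.3 | 84% / 76% / 56% | 0.52 / 0.49 / 0.41 | 1.73 / 1.63 / 1.36 |

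Without the gate, the mean ANCOVA estimate equals the truth (0.50 and 0.30) in every setting, to within simulation error.

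**Step 3: the case of no true effect.** In a separate run with n from 40 to 100 and ρ = .5, the gate opened in about 5% of trials. The estimates it released averaged about 0.27 to 0.45 SD in absolute size.

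**Step 4: conditional consequence for sizing.** Required sample size varies as 1/d². A trial planned on an estimate inflated by ratio r therefore gets 1/r² of the number it needs. The range is 1/1.02² = 0.96 at best to 1/1.73² = 0.33 in the most adverse setting.

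**Step 5: power.** At n = 60 and d = 0.5, the gate against a single-timepoint ANCOVA has power 49% against 59%, 72% against 75%, and 96% against 95%. The gate is modestly weaker at low to moderate correlation and not weaker at high correlation.

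**Step 6: sensitivity to clustering.** The design effect of 2.55 with an assumed 10 per cluster implies an intraclass correlation of (2.55 − 1)/(10 − 1) = 0.17. With that value and n from 40 to 100, the ratio ran from 1.15 to 1.37 at d = 0.5 and from 1.56 to 1.96 at d = 0.2. The direction did not change.

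**The case against.** **An unbiased contrast already exists for every outcome.** The repeated measures ANOVA is ungated, and its cell means give the difference in change from baseline at each follow-up. The standard error of that contrast exceeds the ANCOVA's by a factor of about √(2/(1 + ρ)) = 1.15, 1.08 or 1.04 at correlations of .5, .7 or .85. This stands: what is lost is the adjusted estimate, which is the more precise one, and not all information. But the plan does not commit to reporting the cell-mean contrast or an interval for it.

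**The ANCOVA is a follow-up test, and following up only a positive omnibus test is conventional.** That is how the plan frames it. It is also the only adjusted contrast planned, in a study that lists initial efficacy among its aims.

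**No section says these estimates will size the next trial.** True. The full-size calculation rests on an assumed medium effect. The sizing shortfall is therefore conditional, and the 33% figure is a worst case. The selective availability of estimates does not depend on that use.

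**The size depends on the setting.** Also true. At n = 60, d = 0.5 and correlation .85 the effect is negligible. With all 100 participants complete, an optimistic bound, the estimate at d = 0.5 is withheld in 27%, 8% or under 1% of trials, with mean values of about 0.55, 0.51 and 0.50.

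**Clustering is left out of the main figures.** It is, so they illustrate the mechanism and do not predict this trial's results. The missing cohort term is a separate issue and adds no weight here.

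**Conclusion.** The concern holds. Followed as written, the plan gives baseline-adjusted arm differences for a selected subset of outcomes, and those it gives tend to be too large. For a medium effect at the planned retention, the estimate is missing in 4% to 51% of trials and inflated by 2% to 22%. For a true effect of 0.3 SD, the figures are 43% to 80% and 23% to 61%. At the minimum target of 44, both problems are worse. The direction was the same in every non-null setting tried. The size rests on the assumed correlation, effect pattern, .05 gate and absence of clustering. Because this is a pilot and an unadjusted change contrast can be recovered, the point should be corrected, but it does not undermine the trial. Confidence in the size is moderate.

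**What to change.** Remove the condition. For substance use, craving and PTSD symptoms, report the TI-MBRP minus Standard MBRP difference adjusted for baseline, with its 95% CI, at post-course and at one month, whatever the interaction p-value. Use standard errors that account for the randomized cohort; the plan has no such term and would have to add one. The repeated measures ANOVA can stay as the overall test, with its significance level stated.

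The cost is a wording change and a results table of 3 outcomes × 2 timepoints = 6 adjusted differences. Because the text is in the past tense, it also means a small re-analysis of data already collected. No new data are needed.
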